## 6) Allergies and Adverse Drug Reactions

- a) History of any significant drug allergy (such as anaphylaxis)

## 7) Other Exclusion Criteria

- a) Prisoners or subjects who are involuntarily incarcerated. (Note: Under certain specific circumstances a person who has been imprisoned may be included or permitted to continue as a subject. Strict conditions apply, and BMS approval is required).
- b) Subjects who are compulsorily detained for treatment of either a psychiatric or physical (eg, infectious disease) illness
- c) Inability to comply with restrictions and prohibited activities/treatments as listed in the study protocol
- d) Site personnel or their immediate family
- e) Any contraindications listed in the country-specific label for apremilast

## 5.3 Lifestyle Restrictions

General skin care measures (with above restrictions for topical treatments) that are standard for patients with plaque psoriasis are permitted. Subjects should avoid excessive sun exposure and avoid risks that are known to provoke flare of psoriasis.

### 5.3.1 Meals and Dietary Restrictions

Study treatment may be taken without regard to meals, however, subjects are required to fast for a minimum of 10 hours before visits on which fasting lipid, fasting glucose [REDACTED] samples will be drawn. [REDACTED]

### 5.3.2 Caffeine, Alcohol and Tobacco

No restrictions are required; however, extensive use of caffeine, alcohol and tobacco should be avoided.

### 5.3.3 Activity

No restrictions are required; however, unusual physical exertion should be avoided during the study.

## 5.4 Screen Failures

Screen failures are defined as subjects who consent to participate in the clinical study but are not subsequently randomized in the study for any reason. A minimal set of screen failure information is required to ensure transparent reporting of screen failure subjects, to meet the Consolidated Standards of Reporting Trials (CONSORT) publishing requirements, and to respond to queries from regulatory authorities. Minimal set of screen failure information includes date of consent, demography, screen failure details (ie, eligibility criteria that the subject did not meet), and any serious AEs during the screening period.

#### **5.4.1      *Retesting During Screening or Rescreening***

For laboratory parameters that initially do not meet eligibility requirements, a single retest within the 28-day screening period is permitted before subject is declared a screen failure. This is an effort to find all possible well-qualified subjects. Consultation with the Medical Monitor may be needed to identify whether repeat testing of any particular parameter would be clinically relevant.

The study permits the rescreening (after the end of the initial 28-day screening period) of a subject who discontinues the study as a pretreatment failure (ie, the subject fails to meet eligibility criteria and has not been treated). The subject must be reconsented, will be assigned a new identification number, and a full Screening Visit must be performed again. A subject can only be rescreened 1 time (ie, if the subject fails 1 rescreening attempt, no additional rescreening is allowed). Depending on the timing of rescreening, repeat chest imaging may not be required. Duration of existing treatments and required discontinuation periods shall be considered relative to the new Screening Visit and/or randomization.

The most current result prior to randomization is the value by which study inclusion will be assessed, as it represents the subject's most current clinical state.

## **6            TREATMENT**

Study treatment is defined as any investigational treatment(s), marketed product(s), placebo, or medical device intended to be administered to a study subject according to the study randomization or treatment allocation.

Study treatment includes both Investigational [Medicinal] Product (IP/IMP) and Non-investigational [Medicinal] Product (Non-IP/Non-IMP) and can consist of the following: BMS-986165, placebo, and apremilast.

An IP, also known as IMP in some regions, is defined as a pharmaceutical form of an active substance or placebo being tested or used as a reference in a clinical study, including products already with a marketing authorization but used or assembled (formulated or packaged) differently than the authorized form, or used for an unauthorized indication, or when used to gain further information about the authorized form.

Other medications used as support or escape medication for preventive, diagnostic, or therapeutic reasons, as components of the standard of care for a given diagnosis, may be considered as non-IP. [Table 5](#) shows the study treatments for Protocol IM011046.

**Table 5:** Study Treatments for IM011046

Product Description/Class and Dosage Form	Potency	IP/Non-IMP	Blinded or Open-Label	Packaging / Appearance	Storage Conditions (per label)
BMS-986165 tablet	6 mg	IP	Blinded	Bottle	Store at 15 to 25°C; Store in a tightly closed container; Protect from light
Placebo tablet to match BMS-986165 6 mg	n/a	IP	Blinded	Bottle	Store at 15 to 25°C; Store in a tightly closed container; Protect from light
Apremilast tablet	10 mg*	IP	Blinded	Blister card	Store tablets below 30°C (86°F). Store in original container
Placebo tablet to match apremilast 10 mg	n/a	IP	Blinded	Blister card	Store tablets below 30°C (86°F). Store in original container
Apremilast tablet	20 mg †	IP	Blinded	Blister card	Store tablets below 30°C (86°F). Store in original container
Placebo tablet to match apremilast 20 mg	n/a	IP	Blinded	Blister card	Store tablets below 30°C (86°F). Store in original container
Apremilast tablet	30 mg ‡	IP	Blinded	Bottle	Store tablets below 30°C (86°F). Store in original container
Placebo tablet to match apremilast 30 mg	n/a	IP	Blinded	Bottle	Store tablets below 30°C (86°F). Store in original container

IP = investigational product; IMP = investigational medical product; n/a = not applicable

\*Used for titration Day 1 through Day 3 morning dose

†Used for titration Day 3 evening dose through Day 5 morning dose

‡From Day 5 evening dose onwards.

## 6.1 Treatments Administered

Study treatment will be administered in a double-blind, double-dummy fashion as described in Section 4.1.2. The selection and timing of dose for each subject is as follows:

**Table 6: Selection and Timing of Dose**

Study Treatment	Unit dose strength(s)/Dosage level(s)	Dosage formulation Frequency of Administration	Route of Administration
6 mg QD BMS-986165	6 mg	1 active tablet QD in the morning; 1 placebo titration kit* then 2 apremilast placebo (1 tablet in the morning, 1 tablet in the evening)	oral
30 mg BID apremilast	30 mg	1 active titration kit* then 1 active morning and evening and 1 BMS-986165 placebo once daily in the morning	oral
Placebo BID	n/a	1 placebo apremilast titration kit* then 2 apremilast placebo (1 tablet in the morning, 1 tablet in the evening) and 1 BMS-986165 placebo once daily in the morning	oral

Abbreviations: BID = twice daily; n/a = not applicable; QD = once daily

\*Titration kit is described in Section 6.1.1

### 6.1.1 Titration Kit for Active and Placebo Apremilast

Apremilast will be titrated over 5 days to a maintenance dose of 30 mg BID. To maintain the blind between subjects receiving apremilast and BMS-986165 during the titration period, active apremilast and matching apremilast placebo tablets will be provided. This will be supplied in an 18-day titration kit as follows:

One 10 mg tablet in the morning on Day 1; two 10 mg tablets (one in the morning, one in the evening) on Day 2; one 10 mg tablet in the morning and one 20 mg tablet in the evening on Day 3; two 20 mg tablets (one tablet in the morning, one tablet in the evening) on Day 4; one 20 mg tablet in the morning and one 30 mg tablet in the evening on Day 5; one 30 mg tablet in the morning and one 30 mg tablet in the evening for each Day 6 through Day 18.

## 6.2 Method of Treatment Assignment

Before the study is initiated, each user (at investigative sites) will receive log-in information and directions on how to access the interactive response technology (IRT) system. At the time of the Screening Visit, immediately after informed consent is obtained and before any study-related procedures are performed, the investigative site will access the enrollment option of the IRT system for assignment of a subject number for all subjects, including subjects not subsequently randomized or treated. The subject number is assigned sequentially by the system and will be unique across all sites. All enrolled subjects will be assigned sequential subject numbers. The subject number will not be used for any other subject. If a subject is rescreened, they will be given a new identification number.

At Week 0 (Day 1), subjects who meet all criteria for enrollment at Screening and Day 1 will be centrally randomized in a 2:1:1 ratio to BMS-986165 6 mg QD, placebo, or apremilast 30 mg BID as determined by a computer-generated randomization schedule using IRT. The randomization lists will be generated by the IRT vendor using a permuted block design within each combination of stratum level. The randomization in this study will be stratified by geographic region (U.S., Japan [body weight stratum will not be applied in Japan], China [body weight stratum will not be applied in China], and Rest of World), previous biologic use (for psoriasis, psoriatic arthritis or other inflammatory diseases only; yes/no), and body weight ( $\geq 90$  kg and  $< 90$  kg). As this is designed to be a global study across multiple countries, randomization in each country will be targeted to approximately 35% or less of the total sample size. This change is being implemented to achieve geographical representation across countries and to minimize the potential for any single country to have a disproportionate impact on the overall efficacy and/or safety profile.

After all inclusion/exclusion criteria have been met for a subject, the investigative site will access the IRT on Day 1 for the purposes of randomizing a subject. A treatment group will be assigned by IRT based on the above-described randomization schedule and each subject will be assigned a unique randomization number. In addition, a unique kit number will be assigned to the subject corresponding to the treatment assignment.

A kit will contain adequate study treatment for a 4-week supply. At subsequent visits, when new treatment kits need to be provided, the investigative site will access the IRT to obtain the kit number to assign to the subject. Study treatment will be dispensed at study visits as shown in the Schedule of Activities (Section 1.3).

At Week 16, subjects receiving placebo will be switched in a blinded manner to BMS-986165 6 mg QD.

At Week 24, subjects originally randomized to apremilast 30 mg BID who do not achieve PASI 50 response will be switched in a blinded manner to BMS-986165 6 mg QD. Subjects originally randomized to apremilast 30 mg BID who achieve PASI 50 response at Week 24 will continue to receive apremilast 30 mg BID in a blinded manner. The investigative site and other study personnel will not have knowledge of the PASI 50 score at this visit and will therefore remain blinded.

### **6.3        Blinding**

#### **6.3.1      *Maintaining the Blind***

Blinded treatment assignments will be managed using IRT. Throughout the study, subjects will receive matching placebo (for BMS-986165 and/or apremilast) as needed to maintain the treatment blind. IP supply will be controlled by IRT at each visit.

All tablets are identical in appearance and will be supplied in blister cards or bottles with each daily dose made up of the appropriate combination of active and/or placebo tablets to provide the correct treatment, as shown in Table 5. Investigative site staff, Sponsor and designee personnel, and subjects and their families will remain blinded to treatment assignments.

### **6.3.2 *Circumstances for Unblinding***

Blinding of treatment assignment is critical to the integrity of this clinical study. However, in the event of a medical emergency or pregnancy in an individual subject in which knowledge of the IP is critical to the subject's management, the blind for that subject may be broken by the investigator. The subject's safety takes priority over any other considerations in determining if a treatment assignment should be unblinded.

Before breaking the blind of an individual subject's treatment, the investigator should determine that the unblinded information is necessary, ie, that it will alter the subject's immediate management. In many cases, particularly when the emergency is clearly not related to the IP, the problem may be properly managed by assuming that the subject is receiving active product. It is highly desirable that the decision to unblind treatment assignment be discussed with the Medical Monitor, but the investigator always has ultimate authority for the decision to unblind. The principal investigator should only call in for emergency unblinding AFTER the decision to discontinue the subject has been made.

In case of an emergency, the investigator has unrestricted access to randomization information via IRT and is capable of breaking the blind through the IRT system without prior approval from the Sponsor. After the unblinding, the investigator shall notify the Medical Monitor and/or study director. The method of unblinding for emergency purposes is described in the IRT manual. Subject and unblinded treatment information and the reason for the blind being broken must be recorded on the appropriate study status page of the electronic case report form (eCRF). After unblinding via IRT, the investigator shall notify the Medical Monitor.

In cases of accidental unblinding, contact the Medical Monitor and ensure every attempt is made to preserve the blind. Any request to unblind a subject for nonemergency purposes must be discussed with the Medical Monitor prior to unblinding.

If a subject is unblinded for any reason, the subject will be discontinued from treatment.

### **6.4 *Dosage Modification***

There is no provision for dose-modification of study treatment. If a subject interrupts treatment due to an AE, study treatment can be restarted in consultation with the Medical Monitor.

### **6.5 *Preparation/Handling/Storage/Accountability***

The IP should be stored in a secure area according to local regulations. It is the responsibility of the investigator to ensure that the IP is only dispensed to study subjects. The IP must be dispensed only from official study sites by authorized personnel according to local regulations.

The product storage manager should ensure that the study treatment is stored in accordance with the environmental conditions (temperature, light, and humidity) as determined by BMS. If concerns regarding the quality or appearance of the study treatment arise, the study treatment should not be dispensed and BMS should be contacted immediately.

Study treatment not supplied by BMS will be stored in accordance with the package insert.

Investigational product documentation (whether supplied by BMS or not) must be maintained that includes all processes required to ensure drug is accurately administered. This includes documentation of drug storage, administration and, as applicable, storage temperatures, reconstitution, and use of required processes (eg, required diluents, administration sets).

Guidance and information for final disposition of unused study treatment are provided in [APPENDIX 2](#).

### **6.5.1      *Retained Samples for Bioavailability/Bioequivalence***

Not applicable.

### **6.6          *Treatment Compliance***

Study treatment compliance will be periodically monitored using standard drug accountability procedures (comparing the number of tablets returned to number dispensed, considering the expected regimen and any reported missed doses). Drug accountability will be reviewed by the investigative site staff at each visit to confirm treatment compliance. Site staff will discuss any discrepancies with the subject and remind the subject of the importance of compliance with the assigned regimen. A real-time monitoring platform may be used.

### **6.7          *Concomitant Therapy***

#### **6.7.1      *Prohibited and/or Restricted Treatments***

Prohibited and/or restricted medications during the study are described below. Medications taken within 4 weeks prior to study drug administration must be recorded on the CRF.

- 1) Exposure to any investigational drug or placebo outside of the current study
  - 2) Any concurrent use of strong CYP450 inducers according to the US package insert for apremilast as it may reduce apremilast efficacy. Examples include rifampin, phenobarbital, carbamazepine, and phenytoin, unless it is considered necessary for the subject's welfare and/or treatment of an AE/SAE
  - 3) Use of any medications/therapy that would aggravate psoriasis. These include agents such as lithium, antimalarials (quinacrine, chloroquine, and hydroxychloroquine), propranolol, indomethacin, and quinidine unless it is considered necessary for the subject's welfare and/or treatment of an AE/SAE
  - 4) Use of opioid analgesics unless it is considered necessary for the subject's welfare and/or treatment of an AE/SAE
  - 5) Phototherapy; use of tanning booths or therapeutic sunbathing
  - 6) Any use of biologic medications (eg, adalimumab, etanercept, infliximab, ustekinumab)
  - 7) Any use of oral psoriasis medications (eg, methotrexate, cyclosporine, retinoids, fumaric acid derivatives) for any indication
  - 8) Any use of oral or injectable corticosteroids (prednisone, methylprednisolone, etc.), unless it is considered necessary for the subject's welfare and/or treatment of an AE/SAE
- Note: otic, ophthalmic, nasal, or inhaled corticosteroids within recommended doses and with no systemic effects are permitted

**9)** Any topical medications/treatments, which are used for any indication, that could affect psoriasis evaluation (including, but not limited to, high potency corticosteroids [WHO Classes I-V], >3% salicylic acid, urea, alpha- or beta-hydroxy acids, anthralin, calcipotriene, vitamin D derivatives, retinoids, tazarotene, methoxsalen, trimethylpsoralens, pimecrolimus, and tacrolimus)

Exception: The following topical treatments may be initiated only at Week 24 per investigator's discretion in subjects who have sPGA scores ≥3 (See Section 4.1.4):

- High potency corticosteroids (WHO Classes I-V), >3% salicylic acid, urea, alpha- or beta-hydroxy acids, anthralin, calcipotriene, vitamin D derivatives, retinoids, tazarotene

Note: Low potency topical steroids (WHO Classes VI and VII) are permitted on the palms, soles, face, and intertriginous areas but should not be used within 24 hours prior to any study visit. Bland emollients (defined as emollients without urea or alpha or beta hydroxy acids or other ingredients which are pharmaceutically active) are allowed on all body regions but should not be used within 24 hours prior to any study visit

**10)** Any medicated shampoos that contain corticosteroids, coal tar, >3% salicylic acid, or vitamin D3 analogues

Exception: The above shampoos may be initiated only at Week 24 per investigator's discretion in subjects who have [REDACTED] (See Section 4.1.4).

**11)** Live vaccination

No concomitant medications (prescription, over-the-counter, or herbal) are to be administered during the study unless prescribed for treatment of specific clinical events. Any concomitant therapies must be recorded on the CRF.

The investigator should contact and confirm agreement with the Medical Monitor prior to the administration of any concomitant medications.

### **6.7.2      Permitted Concomitant Medications**

Stable doses of concomitant medication for chronic medical conditions are permitted as long as neither the medication nor the medical condition meet exclusion criteria as detailed in Section 5.2. Dose adjustments of these medications should be avoided during the study unless clinically indicated. If a dose adjustment of these medications should occur, they must be recorded on the Concomitant Medications eCRF or the Procedures and Significant Nondrug Therapies eCRF. The investigator should instruct the subject to notify the study site about any new treatments he/she takes after the start of the study treatment. All medications and significant nondrug therapies (including physical therapy and blood transfusions) administered after the subject starts study treatment must be listed on the Concomitant Medications eCRF or the Procedures and Significant Nondrug Therapies eCRF.

Note: Low potency topical steroids (WHO Classes VI and VII) are permitted on the palms, soles, face, and intertriginous areas but should not be used within 24 hours prior to any study visit. Bland emollients (defined as emollients without urea or alpha- or beta-hydroxy acids or other ingredients which are pharmaceutically active) are allowed on all body regions but should not be used within 24 hours prior to any study visit.

### **6.7.3      *Rescue Medications***

At Week 24, a subject who has an sPGA  $\geq 3$  [REDACTED] may be treated with restricted topicals or shampoos, respectively, as described in Section 6.7.1 at the investigator's discretion. These treatments may only be initiated at Week 24, and not at subsequent time points. A subject who is initiated on these treatments at Week 24 may use them as needed per the investigator's judgment through Week 52.

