### Week 24 activities

[figure not shown]
At Week 24, subjects originally randomized to apremilast who do not achieve PASI 50 response will be switched in a blinded manner to BMS-986165 6 mg QD. Subjects in the apremilast treatment arm who achieve PASI 50 response at Week 24 will continue to receive apremilast in a blinded manner through Week 52.

During the Week 24 assessment, a subject who has an sPGA  $\geq 3$  or ss-PGA $\geq 3$  may be treated with restricted topicals/shampoos as described in the protocol (Section 6.7.1). These treatments may only be initiated at Week 24, and not at subsequent time points. A subject who is provided these treatments at Week 24 may use them as needed per the investigator's judgement through Week 52.

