## 2.5 Changes in Statistical Considerations from the Protocol

The following is a list of the important changes in the SAP from the Statistical Considerations section in the protocol:

- The hierarchical testing order for the key secondary endpoints has been updated and two separate hierarchies have been provided, one for US submission and one for ex-US submission (see [Tables 1](#) and [2](#) in Sec. 6.1.3). The update to the hierarchies are due to emerging information from clinical trials conducted with other agents recently approved for the treatment of psoriasis. The hierarchies presented in this document supersede the one that is in the protocol.

Sponsor: Bristol-Myers Squibb

Protocol no: IM011046

- Key secondary endpoints were added for the comparison of BMS-986165 to apremilast for sPGA 0/1, PASI 75, and PASI 90 at Week 24.
- Imputation methods were updated to remove the prohibited medication/therapy criteria for binary and continuous endpoints.
- The Full Analysis Set was changed from “all subjects who were randomized to receive assigned study treatment” in the protocol to “all subjects who are randomized”.
- The list of relevant protocol deviations provided in the protocol was updated for determination of the Per Protocol population.
- Logistic regression analyses for binary endpoints were removed as these are similar to the CMH analyses.

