#### Imputation Methodology for Week 52 Endpoints (for comparison of BMS-986165 6 mg QD to apremilast)

The key secondary endpoints included in this analysis are the following:

- sPGA 0/1 response with at least a 2-point improvement from baseline at Week 52 and at Week 24

Sponsor: Bristol-Myers Squibb

Protocol no: IM011046

- PASI 75 response at Week 52 and at Week 24
- PASI 90 response at Week 52 and at Week 24

Subjects must meet response criteria at both Weeks 24 and 52 in order to be considered a responder. Those who do not meet response criteria at both weeks will be considered a nonresponder. NRI will be used for the above key secondary endpoints for subjects who:

- Discontinue treatment or study prior to Week 52
- Have missing Week 52 or Week 24 endpoint data
- Switch from apremilast to BMS-986165 at Week 24 for Week 24 PASI 50 nonresponders

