- Time to first loss of PASI 75 among subjects that are PASI 75 responders at Week 24
- Time to first loss of sPGA 0/1 among subjects that are sPGA 0/1 responders at Week 24 where loss of sPGA 0/1 is defined as an sPGA score  $\geq 2$  (sPGA scores are rounded to the nearest whole number)

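### No visible analysis rule accounts for the topical rescue permitted from Week 24, so PASI results after Week 24 can include topical effect

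*Protocol*

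**What the plan says.** Protocol 6.7.1 restricts topical agents that can influence the psoriasis assessment, then makes an exception: "Exception: The following topical treatments may be initiated only at Week 24 per investigator's discretion in subjects who have sPGA scores" of 3 or more. The excepted agents include WHO Class I-V corticosteroids, calcipotriene, vitamin D derivatives and tazarotene. Medicated shampoos have their own exception, with its condition redacted. Protocol 6.7.3 adds: "These treatments may only be initiated at Week 24, and not at subsequent time points", and then: "A subject who is initiated on these treatments at Week 24 may use them as needed per the investigator's judgment through Week 52". SAP 2.1 gives the entry condition as sPGA of at least 3 or ss-PGA of at least 3.

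For the Week 52 key secondary endpoints, SAP 6.1.2.1 requires response at both Week 24 and Week 52. It sets nonresponse for discontinuation, missing data and "Switch from apremilast to BMS-986165 at Week 24 for Week 24 PASI 50 nonresponders". Rescue is not on that list. Protocol 9.4.2.1 made the start of prohibited therapy a nonresponse trigger, but SAP 2.5 states: "Imputation methods were updated to remove the prohibited medication/therapy criteria for binary and continuous endpoints".

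SAP 6.6.1 lists "Time to first loss of PASI 75 among subjects that are PASI 75 responders at Week 24", and a matching sPGA 0/1 endpoint, for subjects randomized to BMS-986165. The censoring rules shown there concern COVID-19 only. SAP 6.3.3.2 counts users of high potency topical corticosteroids at Week 24 and otherwise summarises corticosteroids by drug class.

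**The concern.** Elsewhere the plan treats the same exposure as something that distorts the assessment. Use of such topicals or medicated shampoos within 2 weeks of Day 1 excludes a subject (Protocol 5.2). Use within 2 weeks before the Week 16 assessment removes a subject from the Per Protocol Set (SAP 5.1). After Week 24, open-ended use has no visible analytic consequence.

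The results after Week 24 serve the objectives of superiority to apremilast at Week 52 and over 52 weeks (Protocol Table 4) and describe maintenance of response. If some responders owe their status to a potent topical, those rates and curves describe study drug plus topical, and a reader cannot tell how much of each.

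**Working it through.** **Step 1. Is rescue covered by any visible rule?**

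| Rule | Covers permitted Week 24 rescue? |
|---|---|
| SAP 6.1.2.1, Week 52 nonresponse list | No |
| Protocol 9.4.2.1, prohibited-therapy trigger | Not clearly: rescue is a stated exception to the prohibition |
| SAP 2.5 | Removes that trigger altogether |
| SAP 6.6.1, time-to-loss censoring | COVID-19 only |
| SAP 6.1.5 (by-visit methods) | Not visible in the public document |

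**Step 2. Which endpoints can rescue reach?** In Protocol Appendix 5, sPGA is (E+I+S)/3 rounded, each item 0 to 4. sPGA of at least 3 needs E+I+S of at least 8 (8/3 = 2.67, rounds to 3). sPGA 0/1 needs E+I+S of at most 4 (4/3 = 1.33, rounds to 1). Both cannot hold at one visit. A subject rescued through sPGA of at least 3 is therefore already a nonresponder on the sPGA 0/1 composite and cannot enter time to loss of sPGA 0/1. On the PASI composites only users who were PASI 75 or PASI 90 responders at Week 24 matter: rescue can prolong a response there but not create one. Results with no Week 24 requirement have no such protection. These are the Week 52 endpoints in Protocol Table 4 and the by-week PASI 75, 90 and 100 comparisons with apremilast to Week 52 in SAP Appendix 2.

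**Step 3. Can PASI 75 coexist with sPGA 3?** In Protocol Appendix 6, PASI is the sum over regions of weight × (E+I+S) × area score, with weights 0.1, 0.2, 0.3 and 0.4.
- E = I = S = 3 throughout, area score 4 everywhere: 9 × 4 = 36. Area score 1 everywhere: 9 × 1 = 9. Improvement = (36 − 9)/36 = 75%. sPGA = 9/3 = 3 at both visits. Severity cancels, so the result does not depend on the two scales grading alike.
- With E+I+S of 8 at Week 24, PASI 75 requires a weighted area of at most 0.25 × (baseline E+I+S)/8 of its baseline value: 25% if baseline E+I+S is 8, 28% if 9, 37.5% if 12.
- PASI 90 requires 0.10 × (baseline E+I+S)/8, that is 10% to 15%. Example: 9 × 5 = 45 falling to 9 × 1 × (0.2 + 0.3) = 4.5, which is 90%. This is an extreme pattern.

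**Step 4. The scalp route.** The head has weight 0.1. A head region with E+I+S of 9 and area score 2 contributes 0.1 × 9 × 2 = 1.8 points. The residual allowed for PASI 75 and PASI 90 is 3.0 and 1.2 points at baseline PASI 12, and 5.0 and 2.0 at baseline 20. Scalp treatment can thus decide PASI status near a threshold. Only by this route could a subject who is sPGA 0/1 at Week 24 also be a rescue user.

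**Step 5. Size.** There is no plan figure to reproduce, and no usage rate is given. Shift in an arm = f × g, where f is the share of the arm who are rescue users relevant to the endpoint and g is the share of those whose status depends on the topical. Both are assumptions. With 600 subjects at 2:1:1, the arms are about 300 and 150.

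| f | g | Shift (points) | Of 300 | Of 150 |
|---|---|---|---|---|
| 1% | 25% | 0.25 | 0.75 | 0.375 |
| 5% | 50% | 2.5 | 7.5 | 3.75 |
| 10% | 100% | 10 | 30 | 15 |

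For the composites, f counts only users who were already PASI 75 or PASI 90 responders at Week 24, so it is smaller than for by-visit rates.

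**The case against.** The best defence is that the rescue rule is the same in all blinded arms, and that counting outcomes regardless of permitted rescue is a recognised treatment-policy choice. That stands. It is a reason not to demand nonresponse as the main rule, but not a reason to leave the handling unstated and untested.

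Four stronger readings are tempting, and the documents do not support them.
- **Rescue is never handled.** SAP 6.1.5 and 6.1.3 are not visible, and the time-to-loss endpoints appear only in the COVID-19 section. A rule for by-visit or time-to-loss results may exist. The claim is firm only for the Week 52 list in SAP 6.1.2.1.
- **The comparison is biased toward BMS-986165.** Apremilast subjects who reach PASI 50 but keep sPGA of at least 3 stay on apremilast and may use the same topicals, which raises the comparator rate. Only the single-arm time-to-loss analysis lacks this offset.
- **ss-PGA of at least 3 opens the potent topicals.** Protocol 6.7.1 ties those topicals to sPGA, and the wording of 6.7.3 suggests that the redacted condition leads to shampoos. The SAP sentence merges the two routes but defers to the protocol.
- **Protocol 6.7.1 and 6.7.3 conflict on use before visits.** Low potency steroids "are permitted on the palms, soles, face, and intertriginous areas but should not be used within 24 hours prior to any study visit", with a parallel note for bland emollients. Silence about another class of agent is not a contradiction.

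The worked PASI cases show that the pattern is possible, not that it is common. SAP 6.3.3 also already tabulates concomitant medications by drug class and arm, so some usage data will be reported, although not linked to rescue or response.

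**Conclusion.** The concern holds in a limited form. No visible rule makes permitted Week 24 rescue a nonresponse, a loss or a censoring event. Topical effect can create responses in Week 52 or by-visit results that do not require Week 24 response, subject to the SAP section that cannot be seen. It can prolong response in the PASI 75 composite, rarely in the PASI 90 composite, and in time to loss of PASI 75. It cannot alter the sPGA 0/1 composite or time to loss of sPGA 0/1 for subjects rescued through sPGA of at least 3.

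The size is unknown. The 0.25 to 10 points above follow only from assuming that 1-10% of an arm are relevant users and that 25-100% of them depend on the topical. The direction against apremilast is open; in the single-arm time-to-loss curve the effect can only delay apparent loss. The coprimary endpoints and all Week 16 comparisons precede rescue and are untouched. This is a cheap improvement to the plan, not a fault in its primary analysis.

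**What to change.** In the SAP:
1. Add a sensitivity analysis in which subjects who started a restricted topical or medicated shampoo at Week 24 count as nonresponders at later visits, in both arms. Apply it to the PASI 75 and PASI 90 composites at Weeks 24 and 52, and to Week 52 and by-visit response after Week 24.
2. Add a version of time to loss of PASI 75 that excludes rescue users. Counting rescue start as loss would not work: the clock starts at Week 24 (Protocol 9.4.4) and rescue can start only then, so every such event would fall at time zero.
3. Extend SAP 6.3.3.2 to tabulate all rescue classes, by arm, over Weeks 24 to 52.

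The cost is SAP wording and a little programming from concomitant-medication data already collected on the case report form. Sensitivity response rates may be slightly less favourable. No clinical rule on rescue, or on its timing before visits, is proposed.
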